Studies of tamoxifen in the adjuvant and preventive setting have demonstrated that a decline in MD of approximately 10% is consistently associated with better outcomes . In a case-control analysis nested within the IBIS-I breast cancer prevention trial, Cuzick *et al.*, observed that approximately 46% of tamoxifen-treated women experienced a  $\geq 10\%$  reduction in MD at 12–18 months and these women had a 63% reduction in breast cancer risk (odds ratio [OR] =0.37, 95% confidence interval [CI] =0.20–0.69,  $p=0.002$ ) as compared with all women on placebo (regardless of MD) . In contrast, tamoxifen-treated women with  $<10\%$  reduction in MD did not experience risk reduction compared to all women on placebo (OR=1.13, 95% CI 0.72–1.77,  $p=0.60$ ). Further, several other retrospective analyses have reported that among women with ER-positive breast cancer treated with tamoxifen, those whose MD declined in the unaffected breast , had better outcomes (reduced risk of recurrence  or death from breast cancer ). In contrast, other agents that have shown chemopreventive efficacy, including raloxifene and exemestane, have not been reported to consistently reduce MD .

The original corporate sponsor completed a 6-month study of 4-OHT gel for breast density reduction using 0.05% (w/v) 4-OHT, a less concentrated gel than currently available (0.2% (w/v) gel). Though overall results of this study were nonsignificant, post-hoc analysis of patients with baseline breast density  $\geq 80\%$  ( $n=19$ ; 4-OHT=9; placebo=10) revealed a  $-4\%$  vs. a  $+0.7\%$  ( $p=0.024$ ) change in baseline density following 6 months of treatment for 4-OHT gel 1mg/d per breast vs. placebo, respectively (source NCI TORF FF-2015 document).

Taken together, changes in MD would be an ideal “biomarker” to be evaluated as the primary endpoint in this short-term prevention using 4-OHT gel in high risk women. The duration of 12 months was chosen because most studies referenced above reported mammographic data at least 12 months.

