## 8. CRITERIA FOR EVALUATION AND ENDPOINT DEFINITION

### 8.1 Primary Endpoint

The primary objective of this study is to evaluate mammographic density (MD) changes induced by 4-OHT gel versus placebo in women with mammographically dense breast. Our hypothesis is that 4-OHT will reduce MD. Baseline and 12 months mammogram [or mammograms from Month 13-18 under the COVID-19 contingency plan] will be evaluated for 4-OHT effect using Cumulus software for the primary endpoint evaluation. Analysis will be based on tomosynthesis imaging using the 2D synthetic image.

MD will be classified using BIRADS descriptions on mammographic reports (i.e: predominantly adipose tissue, scattered fibroglandular densities, heterogeneously dense or extremely dense). BIRADS MD assessment is a consistently utilized measure of breast fibroglandular tissue volume, which can be universally followed and reproduced. BIRADS is a scheme for putting the findings from mammogram screening into a small number of well-defined categories. In addition to BIRADS, baseline and follow up MD will be quantified and recorded using semi-automated software, Cumulus, which has been utilized in earlier density assessment studies. Cumulus reading will be centralized with the reader blinded to the timepoint and treatment group.

For the primary endpoint, the densest breast will be used.

At each institution mammographic images will be collected by a study specific data coordinator who will be overseen by the site Investigator. This data coordinator will also ensure that images are collected in usable format with appropriate de-identification. Follow the instructions in Section 10.2 for Collection and Handling of images.

In summary, the effect of utilized software on the density percent assessment is estimated to be minimal. Based on this, we will use:

- a) Downgrading of the baseline reported BIRADS breast density.
- b) Decrease in breast fibroglandular density by 10% or more as assessed by semi- and automated Breast Density software.

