### 13.4 Primary Objective, Endpoint(s), Analysis Plan

The primary objective of this study is to evaluate the change in percent MD (using Cumulus software) from baseline to the week 52 in women applying 4 mg OHT gel versus placebo based on the intent-to-treat principle. The intent-to-treat population is defined as all participants who are randomized and have MD measurements from both baseline and 52 weeks. The primary analysis will be performed comparing the active group versus placebo group per randomization, regardless of the compliance of each participant.

The percent MD is the MD (percent dense area) that is visually estimated using both the mediolateral oblique (MLO) view and the craniocaudal (CC) view as the proportion of the total breast area that was composed of dense tissue (to the nearest 5%). For the study purpose, the densest breast will be the target lesion for the primary endpoint. Breast biopsy for secondary and exploratory endpoints will be performed in the opposite (non-target) breast.

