
We will evaluate if the change of breast density is different in patients with heterogeneously dense (C) vs extremely dense (D) breast at baseline, by incorporating this covariate and its interaction with treatment over time in the repeated measures analysis.

Due to the COVID-19 closures of clinical research activities, a small number of participants (less than 20) will have their month 12 visits by telephone. These participants will continue the randomized treatments and have mammograms in the month 13-18 visits. The measurements of breast density from the month 13-18 (instead of month 12) visits will be used as the primary endpoint. We will first provide summary statistics for the breast density from the month 13-18 visits, from the month 12 visit, and then graphically explore any impact of potentially longer exposures of the treatment on the primary endpoint of mammographic breast density. If appropriate, we will incorporate the timing of the measurement as a covariate in the analysis to estimate the effect of prolonged exposure of the treatment on mammographic breast density. We will also perform a sensitivity analysis by including month 13-18 measures as primary endpoint, and by excluding month 13-18 measures to evaluate the impact of the different timing of measurements on the primary endpoint analysis. For the sample size calculation, we have factored in a 19% inevaluable rate. Based on the current estimate, even including the follow-up delayed caused by COVID-19, the inevaluable rate is still within 19%. Note that patients who were randomized but never started treatments will be replaced if the inevaluable rate is above 19%.

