### 13.5 Secondary and Exploratory Objectives, Endpoints, Analysis Plans

Note: data from Month 13-18 visit instead of Month 12 will be used if participants were seen under the COVID-19 Contingency Plan.

The secondary objectives are:

1. To estimate and compare the percent change in mammographic breast density (using Volpara) from Baseline to Month 12 in women applying 2mg 4-OHT gel per breast versus placebo.
2. To estimate and compare the percent change in mammographic breast density (using LIBRA) from Baseline to Month 12 in women applying 2mg 4-OHT gel per breast versus placebo.
3. To compare the percentage of women who underwent a change in BIRADS category, comparing pre-and post- treatment measurements, for recipients of active agent versus placebo.
4. To conduct subgroup analyses including BIRAD category, menopausal status, cup size, and total breast volume.
5. To estimate percentage of women with  $\geq 10\%$  absolute decrease in quantitative mammographic density percentage between baseline and 12 months, comparing between treated group 2mg per breast 4-OHT gel to placebo based on Cumulus method.
6. To describe symptoms assessed by BCPT Eight Symptom Scale (BESS) questionnaire and laboratory toxicity assessment (Factor VIII (F VIII), Von Willebrand (vWB) factor, Sex Hormone-Binding Globulin (SHBG), lipid profile).
7. To evaluate plasma measurements of 4-OHT and related metabolite levels and factors related to tamoxifen exposure.
8. To evaluate tissue measurements of 4-OHT and related metabolite levels and factors related to tamoxifen exposure.

The exploratory objectives are:

1. To compare the Cumulus vs. Volpara vs. LIBRA breast density measurement methods to estimate percent change in mammographic breast density from baseline to Month 12 in women applying 2mg of 4-OHT gel per breast vs. placebo.
2. To perform correlation of drug concentrations in the plasma and the tissue.
3. To evaluate plasma measurements of Insulin-like growth factor (IGF) pathway members, C-reactive protein (CRP), and estradiol.
4. To compare the 2D natural vs. 2D synthetic breast density measurement using the Cumulus method to estimate percent change in mammographic breast density from baseline to Month 12 in women applying 2mg of 4-OHT gel per breast vs. placebo.
5. To evaluate tissue biomarkers (among women undergoing optional pre- and post-treatment biopsies):  
Terminal duct lobular unit (TDLU) Involution  
Collagen structural changes  

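### Effect modification by baseline density is planned only through the two-level C/D category; a supportive interaction with quantitative baseline Cumulus density should be added beside it

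*Combined protocol and SAP*

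**What the plan says.** Section 13.4 states "We will evaluate if the change of breast density is different in patients with heterogeneously dense (C) vs extremely dense (D) breast at baseline", and gives the method: "by incorporating this covariate and its interaction with treatment over time in the repeated measures analysis". C and D are the two BI-RADS density categories that qualify a woman for entry (section 4.1.2) and one of the two randomisation strata (section 13.2).

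The fourth secondary objective, in section 13.5, is "To conduct subgroup analyses including BIRAD category, menopausal status, cup size, and total breast volume". For density it names only the category. Section 13.5 also allows adjustment for unspecified covariates, mixed models and correlations of density change with other markers, but it names no interaction of treatment with quantitative baseline density.

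That quantity is available. Section 8.1 says that "baseline and follow up MD will be quantified and recorded using semi-automated software, Cumulus", with central reading blinded to timepoint and arm. Section 13.4 defines the primary analysis population as "all participants who are randomized and have MD measurements from both baseline and 52 weeks".

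Section 2.3 mentions density as a possible modifier in a "post-hoc analysis of patients with baseline breast density" of 80% or more, taken from a six-month study of a weaker gel whose overall result was not significant. In 19 women it gives -4% against +0.7% as the "change in baseline density following 6 months of treatment for 4-OHT gel 1mg/d per breast vs. placebo".

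**The concern.** The plan itself asks whether the gel's effect depends on baseline density. It answers with a two-level category taken from mammography reports, under either the fourth or fifth BI-RADS edition. The same attribute is measured on a much finer scale, by one central blinded reading, in every analysed woman. Cutting a graded modifier in two usually loses information, and interaction tests have little to spare in a trial sized for a main effect.

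Section 2.3 says the results will help plan a large national study, for which the relation between baseline density and effect is an obvious design question. If the only planned analysis is the coarser one, the estimate will be less precise than the data allow. A finer analysis chosen after the data are seen would be post hoc, which is also the weakness of the subgroup result in section 2.3.

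**Working it through.** **Inputs from section 13.1.** 64 evaluable women per arm (128 in total), SD of change 8 points, planned difference 4 points (6% against 2%), two-sided 0.05.

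**Assumed, because the documents do not give them.** The share p of women in category D (10% to 50%); an effect that changes by k points per SD of baseline density (k = 1 to 4); a normally distributed baseline; and, in the main calculation, C/D as an exact cut of that baseline. The model is for change at one visit, a simplification of the planned repeated measures model that treats both modifiers alike.

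**The plan's own figure.** Noncentrality = 4 / (8 × √(2/64)) = 4 / 1.414 = 2.83 on 126 df, giving power of 80.1%. The stated 80% reproduces. Also 158 × 0.81 = 127.98, in line with the 128 evaluable women.

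**Continuous interaction.** SE per SD of baseline = 2 × 8 / √128 = 1.41. Noncentrality is k / 1.41 on 124 df. Power is 11%, 29%, 56% and 80% at k = 1, 2, 3 and 4.

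**C/D interaction.** SE = 2 × 8 / √(128 × p(1-p)). At p = 0.20 this is 16 / √20.48 = 3.54. Under a linear effect, the D and C means lie φ(z)/(p(1-p)) SDs apart, where φ is the normal density at the cut z. At p = 0.20 that is 0.280/0.16 = 1.75 SDs. At k = 4 the expected contrast is therefore 4 × 1.75 = 7.0 points, noncentrality 7.0/3.54 = 1.98, and power 50%.

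**Information kept by the cut** = φ(z)² / (p(1-p)). At p = 0.20 this is 0.0784/0.16 = 0.49.

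| Share in D | SE of C/D contrast | Information kept | Equivalent N of 128 | Power k=2 | k=3 | k=4 |
|---|---|---|---|---|---|---|
| 50% | 2.83 | 0.64 | 81 | 20% | 39% | 61% |
| 40% | 2.89 | 0.62 | 80 | 20% | 38% | 60% |
| 30% | 3.09 | 0.58 | 74 | 19% | 36% | 57% |
| 20% | 3.54 | 0.49 | 63 | 17% | 31% | 50% |
| 10% | 4.71 | 0.34 | 44 | 13% | 23% | 37% |
| Continuous | 1.41 per SD | 1 | 128 | 29% | 56% | 80% |

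At k = 1 neither test is useful: 11% for continuous density and 7% to 9% for C/D. Simulation at k of about 4 (4,000 runs per setting) gave 78% to 79% for continuous density, and 59%, 54% and 47% for C/D at 50%, 30% and 20% D.

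**C/D contrast on its own terms.** For a C-D difference in effect as large as the whole planned 4-point effect, power is 29% at 50% D, 20% at 20% D and 13% at 10% D.

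**If the truth is a step at the C/D boundary.** The ranking reverses. For an 8-point step, C/D has 61% power against 35% for the linear term at 20% D, and 80% against about 60% at 50% D.

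**Rounding.** Section 13.4 describes percent density as read to the nearest 5 points. The information kept is s²/(s² + 25/12) for a baseline SD of s: 0.97 at s = 8 and 0.99 at s = 20 (an assumed range). This loss is negligible beside that of the cut.

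**The case against.** The plan's choice is defensible. C/D is the entry category and a randomisation stratum, so its interaction is the natural one to specify, and a category is easy to apply in a later study. The wording of the fourth secondary objective is open-ended, so nothing forbids a further model. All of this stands, and it is why the C/D interaction should stay.

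The gain depends on a graded effect. The documents establish neither a gradient nor a step, and they do not tie the 80% cut in section 2.3 to the C/D boundary. This stands too: the linear term can lose.

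The largest gains need strong interactions. With an average effect of 4 points, k = 4 implies that the gel raises density in about 16% of women (9% at k = 3). It also gives an active-arm SD of √(64 + 16) = 8.9, against the planned common SD of 8. At k = 2 the comparison is 17% against 29% at 20% D, and both tests are weak.

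A reader might infer three stronger things, none of which the documents support:

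- **That the background shows the effect rising with density.** Section 2.3 reports one post-hoc subgroup of 19 women and gives no result below 80%, so it is not an interaction.
- **That imprecise BI-RADS reading makes the gap far larger.** Adding error to BI-RADS alone does widen it. With equal error in both measures (noise SD 0.75 of the density SD, 20% D), simulated power is 33% against 58% at k = 4 and 12% against 19% at k = 2. The documents give no error figure for either.
- **That a null C/D result would be reported as no difference by density.** The plan does not say so, and section 13.8 asks for 95% confidence intervals on response measures.

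**Conclusion.** The point holds as a cheap improvement to a supporting analysis. The only planned look at effect modification by density uses a two-level category, while a finer measurement exists for every woman analysed. Under a roughly linear change in effect, C/D keeps between 34% (10% D) and 64% (50% D) of the information. At 20% D this costs about 12 points of power at k = 2 (17% against 29%) and 30 points at k = 4 (50% against 80%). These figures rest on an assumed share in D, interaction size and linear shape, together with the plan's SD of 8 and 128 evaluable women. Under a step at the C/D boundary the category is the better test, so the two analyses complement each other.

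It would be wrong to conclude that the C/D interaction is an error or should be dropped, or that the primary result is affected: the primary comparison does not use either interaction. Even the continuous test reaches 80% power only at about 4 points per SD, as large per SD as the whole planned treatment effect, so it is exploratory.

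**What to change.** Keep the C/D interaction in section 13.4 and add beside it one supportive, exploratory model:

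- **Outcome:** change in percent density at the primary endpoint visit (Month 12, or Month 13-18 for women seen under the COVID-19 plan), as the mean of the MLO and CC views of the target breast.
- **Terms:** arm, centred baseline Cumulus percent density (mean of the same two views) and their product.
- **Report:** the treatment difference with 95% CI at the 25th, 50th and 75th percentiles of baseline density, with a plot or other check for non-linearity.
- **Interpretation:** state in advance that a non-significant interaction from either model is not evidence that the effect is the same at all densities.

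The cost is a few lines of text and one extra model on data already collected; sample size and the primary test do not change. The downside is one more exploratory analysis, which assumes approximate linearity and is well powered only for a large interaction.

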### **Month 12 [Day 365 ± 30 days]: Telephone Contact**

The following will be performed:

- Adverse events.
- Concomitant medication.
- Premenopausal women should be reminded that they are strongly advised not to become pregnant while on study and should continue using appropriate contraceptive methods.
- Mail or email the 4-OHT Diary to the participant. Ask the participant to record their daily use of agent on the 4-OHT Diary; using a new Diary for each Canister.
- Participants will be asked to extend their gel application and will be reconsented following the CIRB remote consent procedure for the extended gel application.
- Ship or have the participant pickup a new 6-month supply of the study agent.
- Instruct the participant to keep all used canisters and to bring the canisters with all of their completed Diaries to the next in person clinic visit.
- Drug compliance and agent diary review.

- Mail or email the **BESS QUESTIONNAIRE** to the participant ahead of the telephone visit, if possible. Ask the participant to fill it out ahead of the visit, to sign and date the form at the time of completion, and keep it. Collect the information during the visit, if allowed by the institution and if the participant feels comfortable to discuss the responses over the phone. Participants should return the **BESS QUESTIONNAIRE** at their next in person visit. If you were not able to mail/email the **BESS QUESTIONNAIRE** ahead of the telephone visit, collect the information over the phone, if possible. Record the answers.
- Participants will be reminded of the need to reschedule their mammogram within the next 6 months.
- Participants that do not want to extend their gel application should be taken off agent and asked to allow the collection of their next available mammogram for study purposes.

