## 7.4 Evaluation at Completion of Study Intervention

### Month 13-18

The following will be performed:

- Physical exam, including a breast examination.
- Vital signs, weight.
- Laboratory tests will include the following:
  - CBC (hemoglobin, hematocrit, RBC, WBC, platelet count)
  - Total bilirubin
  - AST (SGOT)/ALT (SGPT)
- In women who were considered premenopausal at baseline: FSH, LH, estradiol.
- A urine or serum pregnancy test will be performed. The urine pregnancy test must be done in the clinic. If the pregnancy test result is positive at the 13-18 Month visit, follow the pregnancy to term and complete the Outcome of Pregnancy CRF. Do not take the participant off study until the completion of the pregnancy when the outcome of pregnancy is known.
- Bilateral mammogram. The raw images must be obtained (see instructions in Section 8.1) for study purposes.
- For participants who underwent the baseline breast biopsy, the biopsy will be repeated if participant extended their gel application.
- Blood draw for research biomarkers
- Adverse events.
- Concomitant medication.
- Collect unused study agent.
- Compliance check will be performed by evaluating the participant's agent diary.
- BESS Questionnaire (refer to Appendix E).
- Tobacco and Alcohol use assessment will be performed at Month 12, using the Month 12 questionnaires (see Appendix G "Alcohol and Tobacco Use Assessment Questionnaires – Month 12").
- Participants will be reminded of the need to return for their next annual mammogram (Month 24 + 8 Months), which is their standard clinical high risk follow-up visit.

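### Section 13.4 reads a later COVID-delayed mammogram as longer exposure, but women who decline the gel extension are then off agent, and the plan has no rule for their readings

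*Combined protocol and SAP*

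**What the plan says.** Section 13.4 expects that "a small number of participants (less than 20) will have their month 12 visits by telephone". It describes all of them in one sentence: "These participants will continue the randomized treatments and have mammograms in the month 13-18 visits". It then fixes which reading counts: "The measurements of breast density from the month 13-18 (instead of month 12) visits will be used as the primary endpoint". After summaries and graphs, and only if judged appropriate, it would "incorporate the timing of the measurement as a covariate in the analysis to estimate the effect of prolonged exposure of the treatment". A sensitivity analysis runs the comparison with and without the Month 13-18 readings.

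The COVID-19 Contingency Plan in Section 7 is not so uniform. At the Month 12 telephone contact: "Participants will be asked to extend their gel application and will be reconsented following the CIRB remote consent procedure for the extended gel application". The same list adds: "Participants that do not want to extend their gel application should be taken off agent", and these women are asked to let the study collect their next available mammogram. At the Month 13-18 visit the bilateral mammogram carries no condition, but for women biopsied at baseline "the biopsy will be repeated if participant extended their gel application".

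**The concern.** The two sections describe different sets of women. Section 13.4 has every delayed woman still on her assigned gel at the mammogram. Section 7 foresees some who stopped around Month 12 and were imaged later. It separates the two groups for tissue; Section 13.4 does not separate them for density.

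What is at stake is the estimate of what longer treatment does to density. In a woman who extends, calendar time and time on gel rise together. In a woman who declines, time on gel stops and time since last application rises. A single timing variable cannot stand for both. If the analyst follows Section 13.4 as written, a decliner's months off agent are counted as months of exposure. The trial itself treats persistence of any density reduction after stopping as an open question (exploratory objective 6), so time off agent cannot be assumed equivalent to time on it.

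**Working it through.** **1. The design figure.** Section 13.1 gives mean decreases of 6% and 2%, SD 8%, a two-sided t-test at 0.05 and 80% power. The standardized difference is (6 − 2)/8 = 0.5. The t-test requires 63.77, so 64 per arm, and 64 per arm gives 80.1% power. The stated figure reproduces and is not in dispute.

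**2. How many women.** Fewer than 20 means at most 19. Against the 128 evaluable women of Section 13.1, 19/128 = 14.8%, if all delayed women are evaluable. Against the 158 randomized, 19/158 = 12.0%. Both are ceilings on delayed women. The number who declined is not given and may be zero.

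**3. What timing means in each group.** Take a mammogram at month m, and assume that a decliner stops at Month 12 and is imaged within the Month 13-18 window.

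| Mammogram at month | Extender: months on / off gel | Decliner: months on / off gel |
|---|---|---|
| 13 | 13 / 0 | 12 / 1 |
| 16 | 16 / 0 | 12 / 4 |
| 18 | 18 / 0 | 12 / 6 |

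The timing value is the same across each row, but the exposure is not. The window is itself an assumption for decliners: Section 7 sets no limit on when their next mammogram falls, and the plan does not say whether a reading outside Month 13-18 would count for the primary endpoint.

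**4. Whether other provisions separate the groups.**
- The sensitivity analysis removes all Month 13-18 readings together. If 19 are removed, 128 − 19 = 109 women remain. It shows whether delayed readings matter to the primary result, but not whether on-agent and off-agent readings differ.
- Section 13.5 plans a compliance covariate and a per-protocol analysis. Neither names extension status or time since last application.
- Section 5.6.1 counts a woman as compliant with at least 9 months of use and 75% of days in the interval, and notes that the interval to end of treatment and final mammogram may vary. Take a decliner with perfect use to Month 12. If the interval ends with treatment, her rate is 12/12 = 100%. If it ends at the mammogram, the rate is 12/m, which stays at or above 75% up to m = 12/0.75 = 16. Imaged by Month 16, she is compliant on either reading; after that, it depends on the interval chosen. Compliance status therefore does not identify decliners.

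**5. How much a mix could distort the delayed group.** This is an illustration with two inputs that are not in the documents. Let f be the share of delayed women on 4-OHT who decline, and r the share of the effect that remains off gel at the mammogram. Take the design difference of 4 points as the on-gel effect, and assume that stopping placebo changes nothing. The contrast in the delayed group is 4 × (1 − f × (1 − r)).

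| f | r = 0 | r = 0.5 | r = 1 |
|---|---|---|---|
| 0 | 4.0 | 4.0 | 4.0 |
| 0.25 | 3.0 | 3.5 | 4.0 |
| 0.50 | 2.0 | 3.0 | 4.0 |
| 1 | 0 | 2.0 | 4.0 |

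This is not the timing coefficient, whose model is unspecified. It shows that the distortion can be nil (no decliners, or full persistence) or large within the few women who inform the question.

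**The case against.** The strongest reply is that this concerns a supplementary analysis that may never be run. The timing model is conditional, the text speaks only of potentially longer exposure, and no rule says that a decliner's reading must enter it. Read literally, the paragraph covers only women who continue. The daily diaries and the compliance covariate also give the analyst some means of seeing who stopped. All of this limits the weight of the point. It does not remove the contradiction between the sections, and no provision identifies off-agent readings.

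Three stronger readings are tempting, and the documents do not support them.

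- A reader might infer that off-agent readings damage the primary test and cost it power. Section 13.4 compares the arms as randomized, regardless of compliance, and Section 8.4 keeps women who stop the gel on study for their mammograms. Including these readings is intended. Any dilution is part of that comparison, and the change proposed here would not alter it.
- A reader might infer that all 19 women, or some known share of them, are affected. The documents count telephone Month 12 visits, not refusals.
- A reader might infer that timing will enter as a main effect without an arm interaction, and so estimate only a trend shared with placebo. The plan states no form for that model. Section 13.4 does use a treatment interaction for baseline density category, so the omission cannot be assumed.

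It is also fair to say that replacing timing by months on gel, even with an arm interaction, would not give a randomized answer. Extension is chosen after randomization and may depend on tolerability, and fewer than 20 women across both arms inform the range beyond Month 12.

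**Conclusion.** The point holds in a limited form. Section 13.4 says that all women with a telephone Month 12 visit continue treatment, and treats later timing as longer exposure. Section 7 allows some of them to be off agent when imaged. For those women the planned interpretation is wrong, and nothing in the plan separates them.

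The reach is at most 19 women, and the number who declined is unknown and possibly zero. What is affected is the conditional prolonged-exposure estimate and any summary that describes the Month 13-18 readings as longer treatment. The primary randomized comparison stands as planned. The conclusion rests on the text of the two sections; only the illustrative range in step 5 needs outside assumptions.

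**What to change.** Before unblinding:

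1. Reconcile Section 13.4 with the Month 12 telephone contact and Month 13-18 visit in the contingency plan. State how delayed readings from women who stopped are handled, including a next available mammogram that falls outside Month 13-18.
2. For each delayed mammogram, derive extension status, months on gel and months since last application from off-agent dates and diaries.
3. Restrict any prolonged-exposure summary or timing model to on-agent readings, or define exposure by actual use instead of mammogram date. Label the result exploratory and non-randomized.
4. Add one sensitivity analysis that excludes only off-agent delayed mammograms, beside the planned one that excludes all Month 13-18 readings.
5. Leave the primary comparison unchanged, with all women who have both readings included as randomized.

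The cost is some SAP wording, three derived variables from data already collected and one extra analysis run. The exposure estimate will be imprecise because few women inform it, and the report should say so. No clinical rule, sample size or data collection changes.
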